Data Safety Monitoring Board (DSMB): The DSMB will consist of three experienced clinicians to exercise oversight of the safety of trial participants. It will be chaired by [name] (Professor of Internal Medicine, UT Southwestern Medical Center), review periodic safety reports prepared by the trial biostatistician ([name]), request additional data/information (if necessary), and advise the trial Executive Committee regarding continuation/discontinuation of the study.

The External Medical Safety Monitor (EMSM, [name]) will closely monitor the incidence rates of all adverse events reported, whether serious or not, throughout the study, and will alert the DSMB if a trend is observed. A summary of all AEs and SAEs, a summary of all reports, and a coded list of all subjects who were terminated from the study due to study-related adverse events, will be included in reports submitted by the DMSB to the IRBs. An annual report will be submitted to the IRBs at all participating sites.

Clinical performance sites will report all fatal events, unanticipated problems and other serious adverse events and suspected adverse reactions to the Data Safety Monitoring Board (DSMB) and IRB by secure email **within 24 hours of first knowledge of the event**. Additionally, all current study data for that particular subject will be entered to allow for timely review by the EMSM, [name].

11. Procedures to Maintain Confidentiality:

Any time information is collected; there is a potential risk for loss of confidentiality. Every effort will be made to keep information confidential; however, this cannot be guaranteed.

Privacy of individuals: The privacy of individuals will be protected by using confidential surroundings for all communications, eliciting and honoring requests for the inclusion and exclusion of family members and partners and following the institutions' codes for ethical and professional conduct of research and patient-centered care.

Confidentiality of data: No personally identifiable information will be recorded outside the electronic medical record. Only those individuals with rights to access the patient's electronic medical record will know the identity of the study subjects. While no efforts at security are completely free of risk, this approach is such that the risk of accidental exposure is negligible.

12. Potential Benefits:

The potential benefits to every subject participating in the clinical trial are related to receiving optimal patient-centered care for their condition. This includes ensuring the mobilization of available resources for rehabilitation programs and the education of all involved patients and their families on the possible consequences of alcohol consumption, particularly in high risk sub- populations. While ideally occurring in the care of all patients with alcoholic hepatitis, the study team will provide patients with the personal healthcare navigation assistance that is not available to every individual.

There may be immediate additional benefits to those in the active study arms if the outcomes are favorable. If the outcomes are favorable, all patients with severe alcoholic hepatitis may benefit from extrapolation of the findings. If the outcomes are negative, other subjects will be protected from the risks of treatment that has no additional benefit to convey.

There is a potential societal benefit in the general outcomes of the clinical trial with respect to alcohol consumption, alcoholism and alcoholic liver disease. In addition, the potential financial benefits of a successful program are substantial.

13. Biostatistics:

Sample size for study of patients with moderate acute alcoholic hepatitis

To compare change from baseline in the two groups of moderate AAH patients, we find that a two-sided two sample t-test of change in MELD score from baseline (mean=17.0) to 30 days with an overall sample size of 108 patients (54 in each treatment group) achieves 80% power with an alpha level of 0.05 to detect a difference in mean change of MELD score of 5.0 in the control group compared to a mean change of 8.0 in the intervention (probiotic) group with a common estimated group MELD score standard deviation of 5.559.

Adjusting for a total of 20% withdrawal, lost to follow-up or non-evaluable, we have $n^* = 108 / (1 - 0.20) = 108 / 0.80 = 136$ patients total or 68 patients in each treatment group. We expect that, in a multivariate model, we will have the power to detect smaller treatment group differences due to the partition of the variance among the predictors.

Statistical analysis plan: Our primary analysis of change in MELD score from baseline to 30 days will be an unadjusted comparison of change (Day 30 – Baseline) using a standard two- group t-test at a two-sided alpha level of 0.05 with appropriate adjustment for unequal variances. We will also conduct secondary analyses to further investigate factors that influence the change as well as adjust for any imbalances in patient characteristics and covariates between treatment groups. Our initial model will be an Analysis of Covariance (ANCOVA) model with change in MELD score as the outcome and with treatment group (0=control, 1=probiotic) and baseline MELD score as predictors. Additional models will include patient characteristics such as age, gender, time since diagnosis as well as other covariates such as ALT, AST, and other laboratory measures at baseline. Finally, as it is likely that MELD score can be calculated throughout the duration of the study, we will use mixed models to analyze the longitudinal MELD score data. Mixed (random effects) models are used to adjust for the inherent correlation among the laboratory (and, thus, MELD score) measures on the same patient. We will consider treatment as a fixed effect, but most other factors as random effects. The model will also include a time metric, so that, rather than the change from baseline, we can use the coefficients of the times as estimates of the change from baseline (time=0), adjusted for the other factors in the model. So, for example, if MELD score is calculated at Days 0, 7, 14, 21, and 30, the model might look like: $MELDt = \beta_0 + \beta_1*tx + \beta_2*gender + \beta_3*age + \beta_4*Day7 + \beta_5*Day14 + \beta_6*Day21 + \beta_7*Day30$ where $MELDt$ = MELD score at time t ($t=0, 7, 14, 21, 30$), $\beta_0 \dots \beta_7$ = regression coefficients, tx = treatment (0=control, 1=probiotic), $gender$ = patient's gender (0=female, 1=male), age =patient's age at last birthday, $Day7$ = MELD score at Day 7 (0=No, 1=Yes), ..., $Day30$ = MELD score at Day 30 (0=No, 1=Yes). This implies that the baseline MELD score is represented by $Day7=Day14=Day21=Day30=0$. Interpreting this model, which makes maximum use of all available MELD scores, the coefficient β_4 is the estimate of the change in MELD score from baseline to Day 7, β_5 is the estimate of the change in MELD score from baseline to Day 14, etc. By combining all of the information into a single model, we can adjust the MELD score changes for other factors as well as test for a difference in the slopes of the changes between the two treatment groups. The model can, of course, be extended beyond 30 days if measures are available. The fit of the model will be assessed primarily through the likelihood ratio test of the fitted model to the intercept only model. All coefficients will be tested for significance at a critical level of $p=0.05$.

Sample size for study of patients with severe acute alcoholic hepatitis

Using the Lakatos approach(19) to estimating the sample size for a log-rank test, we find that a two-sided logrank test with an overall sample size of 130 patients (65 patients each of the control and treatment groups) achieves 80.0% power at a 0.05 significance level to detect a hazard ratio of 0.4447 when the proportion surviving at 6 months in the control group is 0.64 and 0.82 in the treatment group. The total study duration is 2.5 years of which subject accrual (entry) occurs in the first 2 years. We assume that the accrual pattern is uniform throughout the accrual period and that the proportion drop-out in each group is 0.10 during the 6 months with no treatment cross-overs. As a sensitivity analysis of these estimates, we used the Lachin- Foulkes approach⁽²⁰⁾, a slightly less flexible approach and, with the same assumptions as above, we estimate 53 patients in each group, reasonably close to the Lakatos estimates. Thus, to be conservative in our estimates, we will set our

sample size as 130 patients total or 65 patients in each treatment group. PASS II (NCSS, Kaysville, Utah) was used for all sample size calculations⁽²¹⁾.

Statistical analysis plan: Our primary analysis of this outcome will be the unadjusted log-rank test of the Kaplan-Meier survival estimates for the two treatment groups at a two-sided alpha level of 0.05 with survival censored at 6 months. Secondary analysis will use a Cox proportional hazards regression model (with survival censored at 6 months) to adjust the treatment difference in survival for patient characteristics (e.g., age, gender, time since diagnosis) and other covariates (e.g., ALT, AST, other lab measures). Predictors will be added to the model using reference cell coding, as with the mixed models above. The Cox model generates estimates of the hazard ratio for each factor compared to the reference level; e.g., for male patients vs. female patients, assuming gender = 1 for male and 0 for females, a hazard ratio of 1.25 indicates that males have a 25% higher probability of death overall by 6 months compared to females. We can also add time-dependent covariates to the model, such as ALT levels at 2 and 4 months, to estimate their predictive value for mortality. To assess the fit of the model, we will use Nagelkerke's R² constructed from the ratio of the likelihoods for the fitted model to the intercept only model. As further secondary analysis, we can eliminate the survival censoring

at 6 months and test the overall survival throughout the duration of follow-up.

General analysis plan for experiments with fold change as the outcome: Initial analyses will be descriptive in nature, allowing for investigation of appropriate normalization approaches. Initial comparative analyses of fold-change between treatment groups (or between other groups of interest) will be through a standard two-group t-test at the p=0.05 level with appropriate adjustment for unequal variances. If the fold change data are longitudinal in nature, we will use mixed (random effects) models to estimate the change in fold-change over time. In these models, fold-change at each time point will be the outcome with treatment (or other group indicator) and time as predictors. Additional patient characteristics can be added to the model to create adjusted estimates of treatment (or other group) differences. Mixed models can adjust for the correlation due to measures within patients and due to repeated microarrays at each time point.

References

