We will utilize published models for predicting mortality in patients with AAH to stratify patients

based on severity. Although previous studies of treatment for severe AAH utilized 30-day mortality as an endpoint, 6-month mortality is a more relevant outcome, in part because most transplantation programs require 6 months of abstinence before active listing. Furthermore, the number of deaths between 6 and 12 months in abstinent patients is low compared to the number in the first 6 months. Patients will be stratified into those with Model of End-stage Liver Disease (MELD) score ≤ 20 and MELD ≥ 20 . Those stratified into the moderate group are described in a separate application. The primary difference between the Maddrey discriminant function (DF) and the MELD is that the latter includes creatinine. We propose to use the MELD score to stratify for severity but require that patients in the severe group also have a DF > 32 , to avoid including patients with chronic kidney disease, not hepatorenal syndrome.

Specific Aim 1 = Randomized controlled trial for severe acute alcoholic hepatitis: MELD ≥ 20

: Patients with severe AAH will be randomized equally into two arms. Patients with MELD 20-25, patients with MELD 26-31, and patients with MELD \geq 32 will be randomized separately into two equal arms to ensure comparable severity in the three groups. The trial will also be double-blinded by re-packaging all oral medications into capsules to ensure that each group receives an equal number of capsules each day for the entire duration of the study.

Patients will be treated with pentoxifylline 400 mg three times daily for 28 days PLUS zinc supplements for a total of 6 months (Group A) or methylprednisolone 32 mg daily for 28 days PLUS placebo capsules daily for the remaining 5 months (Group B). An injection of either anakinra (100 mg), Group A or a placebo (Group B) will be given subcutaneously each day for 14 days. Patients, investigators and physicians involved in the care of the patients will be blinded as to the treatment.

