Sampling plan: The sample size was calculated based on the analysis of patients with alcoholic liver disease in the (SRTR) database, accounting for drop-out, lost-to-follow-up and non-evaluable results and including a factor for possible non-representativeness of the original database. In addition, preliminary data for 114 patients meeting criteria were used in the calculations and stratification decisions.

4. Criteria for Inclusion of Subjects:

- a. Ability to provide informed consent by subject or appropriate family member
- b. Age between 21-70 years
- c. Recent alcohol consumption > 50 g/d for > 6 months, continuing within two months before enrollment
- d. At least 2 of the following symptoms or signs of acute alcoholic hepatitis: Anorexia, nausea, RUQ pain, jaundice, leukocytes, hepatomegaly, AND
- e. Elevation of AST ≥ 50 U/L, but < 500 U/L at the time of admission or within 3 days of baseline visit; AST $>$ ALT and ALT < 200 U/L; total bilirubin > 3 mg/dL ANDf. Liver biopsy showing alcoholic hepatitis (steatohepatitis) OR ultrasound of liver showing increased echogenicity OR CT scan showing decreased attenuation of liver compared to spleen or MRI showing fatty liver (decreased signaling intensity on T1 weighted images). If the liver biopsy (done within 60 days of inclusion) confirms diagnosis of AAH then inclusion e will be waived.
- g. Model for End-Stage Liver Disease (MELD) ≥ 20 and Maddrey ≥ 32
- h. Willingness to utilize two reliable forms of contraception (both males and females of childbearing potential) from screening through the first six weeks of the study

5. Criteria for Exclusion of Subjects:

- a. Hypotension with BP $< 80/50$ after volume repletion
- b. Pregnancy; incarceration; inability to provide consent or lack of appropriate family member

- c. Signs of uncontrolled systemic infection: Fever $> 38^{\circ}\text{C}$ and positive blood or ascites cultures on appropriate antibiotic therapy for ≥ 3 days within 3 days of inclusion
- d. Acute gastrointestinal bleeding requiring > 2 units of blood transfusion within the previous 4 days
- e. Undue risk from immunosuppression: Positive HBsAg; a positive skin PPD skin test, a positive quantiferon, or history of treatment for tuberculosis; history of any malignancy except skin cancer but including hepatocellular carcinoma; known HIV infection

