- Alcohol usage in the past 60 days prior to assessment specifically and the pattern of chronic usage.
- Review inclusion and exclusion criteria
- Collection of blood for hematology, coagulation, clinical chemistry to include amylase and lipase, ammonia, and in female patients, a pregnancy test.

- Physical examination, including height, weight (body mass index will be calculated based on these variables), and vital signs (systolic and diastolic blood pressure, pulse rate, respiratory rate and body temperature)
- Ultrasound or cross –sectional imaging of the abdomen. This is standard of care in patients hospitalized with alcoholic hepatitis.

Study treatment:

Patients will be randomized to receive 28 days of methylprednisolone 32 mg daily OR therapy that includes a combination of anakinra (interleukin-1 receptor antagonist, IL-1 RA) 100mg by subcutaneous injection daily for 14 days plus pentoxifylline 400 mg orally three times daily for one month PLUS zinc supplements (220 mg of zinc sulfate) given orally for 6 months.

Assessments at baseline and during study treatment:

Study day 0 – baseline (within 48 hours of study enrollment)

- Complete collection of all baseline history. Review of alcohol use history.
- Complete collection of all indicated standard of care laboratory evaluations (chemistry, hematology, coagulation, urine, microbiology, viral, and TB testing) .
- Ascites evaluation, if present.
- Collection of baseline research testing to include urine, blood, DNA and stool testing.
- Collect prior and concomitant medications.
- Clinical assessment to include vital signs and physical exam details.
- Nutritional assessment with a hand grip dynamometer

Treatment day 1 – time zero (alternatively note this as treatment day one with no time and above as study day 1 baseline)

- Begin continuous AE review and reporting
- Begin subcutaneous injected study medication or placebo injection
- Begin dosing of oral study medications (pentoxifylline 400 mg 3 times daily PLUS zinc sulfate 220 mg once daily)/placebo or oral methylprednisolone/placebo preparation

Treatment day 2:

- Inpatient assessment to include:
 - Review baseline history for changes. Review alcohol intake history.
 - Collection of prior and concomitant medications
 - Clinical assessment including vital signs and physical exam details
 - Collection of blood for clinically indicated laboratory studies.
 - Collection of research laboratory studies including urine and blood.

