Standard	Clinical assessment	x	x	x	x	x	x	x	x	x	x
	Alcohol intake	x	x	x	x	x	x	x	x	x	x
	Liver panel (bilirubin, alkaline phosphatase, AST, ALT) and GGT	x	x	x	x	x	x	x	x	x	x
	Serum electrolytes, creatinine, BUN	x	x	x	x	x	x	x	x	x	x
	Serum albumin, total protein	x	x	x	x	x	x	x	x	x	x
	Prothrombin time, INR	x	x	x	x	x	x	x	x	x	x
	Complete blood count	x	x	x	x	x	x	x	x	x	x
	Haptoglobin	x									x
	Lipid panel	x									x
	Amylase, lipase	x									
	HIV	x									
	HAV Ab, HBsAg, HBcore Ab (total)	x									
	HCV Ab	x									
	PPD	x									
	Blood cultures x2	x									
	Urine culture & urinalysis	x									
	24 hour urine (Na, K, creatinine, protein)	x									
	Urine toxicology	x									
	Ascites for albumin, total protein, cell count and differential (if present)	x									
	Ascites culture	x									
	Stool studies (if diarrhea): C. difficile, culture	x									
	Complete abdominal ultrasound or cross-sectional radiology	x									x
Research	Gut permeability studies	x ‡				x		x			x
	Serum zinc, urine zinc	x				x		x			x
	Stool (DNA microbiome)	x						x			x
	Urine (KIM-1)	x	x day2	x		x		x			x
	Biomarkers = Cytokines	x	x day2	x		x		x			x

	DNA = Pharmacogenomics	x									
	Serum micro RNA	x		x		x		x			x
	Monocyte prep (U Mass, U Louisville)	x		x							x
Blood	Research total volume = 179 mL	45		30		37		30			37
	SOC total volume = 208 mL	82	14	14	14	14	14	14	14	14	14
	Combined = 387 mL = 26 tbspns	117	14	44	14	51	14	44	14	14	51

- * clinically indicated; †± 2 weeks ‡ within first 28 days for non-ICU patients

Sub-Study Procedures

1. Optional Natural History (minimal risk with urine and blood collection): All screened subjects meeting inclusion and exclusion criteria below or declining consent to randomization will be invited to join this study of the natural history of severe acute alcoholic hepatitis. The natural history of patients with severe alcoholic hepatitis is not well documented in the current era. Prospective collection of data in parallel with the randomized study subjects has great potential value. Every patient who agrees and gives consent will be seen in follow-up as clinically indicated. At each visit that coincides with collection of samples for research, or as close as possible to Baseline, Day 7, Day 28, Month 3 and Month 6, the subjects will be offered the opportunity to participate. Patients may also be asked to participate in the natural history study as a one-time draw at the day of consent.

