4. Criteria for Inclusion of Subjects for Natural History Specimen Collection:

- a. Ability to provide informed consent by subject or appropriate family member
- b. Age between 21-70
- c. Suspected or proven alcoholic liver disease

5. Criteria for Exclusion of Subjects for Natural History Specimen Collection:

- a. Pregnancy; incarceration; inability to provide consent or lack of appropriate family member
- b. Signs of uncontrolled systemic infection: Fever $> 38.0^{\circ}\text{C}$; positive blood or ascites cultures on appropriate antibiotic therapy for >3 days within 3 days of inclusion
- c. Evidence of acute pancreatitis: CT evidence or amylase or lipase $>5 \times \text{ULN}$
- d. Evidence of other liver diseases such as autoimmune hepatitis, primary biliary cirrhosis, primary sclerosing cholangitis, Wilson disease, biopsy proven hemochromatosis, alpha-1-antitrypsin deficiency

Over the entire 6 months study period 387 mL of blood will be drawn, comprising 208 mL for standard of care tests and 179 mL for research studies.

Optional DNA Blood Sample Collection: A biorepository can serve as a national resource for all studies related to acute alcoholic hepatitis. A major goal of the U-01 consortium is to share clinical samples. Our research group will use the samples and share with others for future studies on biomarkers for AAH severity/outcome, cost analysis, rationales for new therapies, etc. Blood and tissue samples will be collected as indicated in the table. Samples for DNA preparation will be shipped to the Cleveland Clinic and specimens will be shipped to those translational sites that are studying biomarkers or pharmacogenomics (U Mass, U Louisville). Specimens will only be identified by the unique study number. De-identified data obtained from the various pharmacogenomics, miRNA and transcriptosome screens will be placed on the website of the U-01 consortium and be available to the U-01 investigators throughout the study.

The amount of blood that would be collected is 8 mL (2 tbspsns) and it will be stored at the Cleveland Clinic Foundation as part of the NIH Tissue and Biorepository for Alcoholic Hepatitis Studies.

7. Sources of Research Material: Specimens: Blood, urine, stool

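### Drug-trial exclusion c, read literally, does not exclude an afebrile patient whose culture is still positive on antibiotics; at best the wording is ambiguous on a patient-safety rule

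*Combined protocol and SAP*

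**What the plan says.** Section 5 of the protocol (exclusion criteria for the drug trial), item c, has a lead-in about signs of systemic infection that is not under control. It then gives fever above 38 °C "and positive blood or ascites cultures on appropriate antibiotic therapy for ≥ 3 days within 3 days of inclusion".

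Item e of the same list excludes patients for whom immunosuppression would be too dangerous: "Undue risk from immunosuppression: Positive HBsAg; a positive skin PPD skin test, a positive quantiferon, or history of treatment for tuberculosis". It goes on to malignancy and known HIV. It does not mention a bacterial infection that persists on treatment.

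The natural history sub-study has its own exclusion list. Item b there has the same lead-in and the same fever threshold, then a semicolon, then "positive blood or ascites cultures on appropriate antibiotic therapy for >3 days within 3 days of inclusion". It differs from the drug-trial item in the connector and in the antibiotic duration (more than 3 days, rather than 3 or more).

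An enrolled patient receives either methylprednisolone 32 mg daily for 28 days, or anakinra 100 mg with pentoxifylline and zinc. The anakinra or placebo injection "will be given subcutaneously each day for 14 days" (section 3, Specific Aim 1).

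**The concern.** Bacteria still growing in blood or ascites after 3 or more days of appropriate antibiotics are good evidence that an infection is not controlled, whatever the temperature. If fever is also required, the criterion misses the afebrile patient in that position, who would then be eligible for one of two regimens that each contain a drug with a listed risk of serious infection.

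The protocol's own reasoning makes this uncomfortable. The Background gives avoidance of infection risk as part of the case for the new regimen, and item e excludes a patient for a positive tuberculin test alone. It would be odd to accept a patient with a culture-positive infection that is failing treatment.

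What is at stake is the safety of individual patients and uniform application of the rule across sites.

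**Working it through.** No arithmetic applies. The check is to read item c as a logical condition, compare it with its counterpart in the sub-study, and look for any other rule that covers the patient.

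**Step 1: item c under each reading.** *Positive* means a blood or ascites culture positive on at least 3 days of appropriate antibiotics.

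| Patient | c, both signs required | c, either sign enough | Natural history item b, semicolon read as *or* |
|---|---|---|---|
| Fever, positive | excluded | excluded | excluded |
| No fever, positive | **not excluded** | excluded | excluded once past 3 days of antibiotics |
| Fever, not positive | not excluded | excluded | excluded |
| No fever, not positive | not excluded | not excluded | not excluded |

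The second row is the point at issue. A variant of the first reading, in which c describes a culture-proven infection with fever persisting despite treatment, leaves that patient uncovered as well.

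**Step 2: which reading do the eligibility lists favour?** Elsewhere in them *and* is a true conjunction. Inclusion g joins the MELD and Maddrey thresholds with it, and section 3 confirms that both are required. Alternatives are joined by *or* (exclusion g, on pancreatitis) or separated by semicolons (exclusions b and e). By that usage the drug-trial item requires both signs, and the natural history item requires either.

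**Step 3: does another exclusion cover the patient?**

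- a: hypotension after volume repletion, so it catches the patient only if also hypotensive.
- b: pregnancy, incarceration, consent.
- d: gastrointestinal bleeding.
- e: hepatitis B, tuberculosis, malignancy, HIV.
- f: recent immunosuppressive treatment.
- g: pancreatitis.
- h: other serious organ disease and other liver diseases.
- i: creatinine.

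None does. The list has no general exclusion at the investigator's discretion, and the study procedures contain no rule that withholds study drug because of a positive culture.

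**Step 4: what would the patient be exposed to?** In section 9 the methylprednisolone table places infection in the serious row and the frequent column (over 20% of subjects), at 1.5 times the risk in controls. The anakinra table lists serious and life-threatening infection as occasional, at 2 to 3%. The risk therefore arises in either arm.

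**The case against.** The strongest reply is that the lead-in of item c is itself the criterion and *and* merely lists its signs. A culture still positive on appropriate therapy is then such a sign, and the patient is excluded. The semicolon in the sub-study, under the same lead-in, supports this as the intent. This stands as a possible reading, and it is why the defect is ambiguity rather than a proven hole. It does not settle the matter: it departs from how *and* is used elsewhere in the eligibility lists, and it would also make fever alone an exclusion, although the Background notes that alcoholic hepatitis itself sometimes causes fever.

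That last fact may explain a deliberate *and*. It is a good reason not to exclude on fever alone. It is no reason to admit a patient with a persistently positive culture.

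The treating team might keep such a patient out, since the primary physician must agree before the patient is approached (section 8). That is a practical safeguard but not an infection rule. The safety monitor, the DSMB and the 24-hour reporting of serious events limit harm only after dosing has begun.

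A reader might infer three stronger claims that the document does not support.

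- *That infection would go undetected because no culture is among the screening procedures.* "Blood cultures x2" is scheduled at Day 0, along with ascites culture. Hepatitis B, tuberculin and HIV tests are likewise scheduled only at Day 0, yet exclusion e relies on them. The patient described here also has a known positive culture already.
- *That the trial exposes such patients to more infection risk than usual care.* Section 9 calls methylprednisolone standard care and gives it the higher infection frequency category. Only the anakinra exposure is specific to the trial, and the tables do not address patients who are already infected.
- *That the trial's result is biased or its power reduced.* Nothing in the wording of item c implies either.

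**Conclusion.** The concern holds as a drafting defect in a safety criterion. Followed literally, the stated rule admits an afebrile patient with a culture still positive on at least 3 days of appropriate antibiotics. On the looser reading it does not. Two versions of the criterion within one protocol differ in connector and in duration, so sites cannot tell which is meant.

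The conclusion rests on the wording alone and on there being no other exclusion that covers the patient. The patient is a narrow case: afebrile, not hypotensive, re-cultured and still positive. The document gives no basis for estimating how many there would be. The sample size and the primary log-rank comparison are unaffected. The criterion should be amended because the potential harm is serious and the correction is simple.

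**What to change.** Reword exclusion c so that a blood or ascites culture still positive after at least 3 days of appropriate antibiotics, within 3 days of inclusion, excludes or defers the patient regardless of fever. Whether fever alone should exclude is for the investigators to decide, given that the disease can cause it. For that reason a bare change from *and* to *or* is not recommended, since it would decide that question by accident.

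The cost is a one-sentence amendment and no new type of test, because blood and ascites cultures are already scheduled at Day 0. Some patients would be excluded or deferred who would otherwise have entered; their number cannot be estimated from the document. Deferral is not free in a disease for which the Background reports 20% mortality at 30 days on placebo, but it would fall only on patients whose infection is failing treatment.
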